### Individual blood pressure responsiveness to isometric handgrip training

We aim to conduct an exploratory analysis of the individual BP responsiveness to isometric handgrip training. Participants will be classified as showing relevant (responder) or negligible (non-responder) training-related hypotensive effects using the ROPE + HDI decision rule to reject or non-reject the null – a Bayesian method (38,39). Briefly, this method estimates the percentage of the highest density interval (HDI, like CI in frequentist statistics) within the range of values around the null – region of practical equivalence (ROPE). This estimated percentage corresponds to different levels of significance that will guide the training-related hypotension individual response classification with non-responders defined as > 99 %, likely responders < 5%, and responders < 1% of HDI within the ROPE (38,39).

The HDI calculated as an 89% credible interval will be derived from each participant's posterior normal distribution obtained from 1000 simulations based on the individual pre-to-post change in SBP and DBP (delta) and respective standard deviations calculated as TE/2, where TE is the technical error calculated as CV/2 \*100) (38–40). Individual normal distributions will be derived using the R's rnorm function. We will estimate the ROPE as 20% of the baseline SBP and DBP standard deviations in each group (sex) and this represents the smallest worthwhile difference (41–43). Both the HDI and the ROPE will be computed with R package bayestestR (44). Participants will then be classified according to the ROPE + HDI decision rule. This method of classifying responders mitigates some pitfalls of the traditional response threshold binary classification, such as not accounting for within-participant measurement error variability associated with blood pressure or the magnitude of group differences in mean response (40,41,45).

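### The written responder rule has no condition on the sign of the blood pressure change, so a clear rise meets the cut-off for a hypotensive responder

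*Combined protocol and SAP*

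**What the plan says.** All the relevant text is in the section on individual blood pressure responsiveness to isometric handgrip training, which presents the analysis as exploratory.

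- **Purpose.** "Participants will be classified as showing relevant (responder) or negligible (non-responder) training-related hypotensive effects". The target is a fall in blood pressure.
- **Statistic.** The method "estimates the percentage of the highest density interval (HDI, like CI in frequentist statistics) within the range of values around the null".
- **Cut-offs.** "non-responders defined as > 99 %, likely responders < 5%, and responders < 1% of HDI within the ROPE".
- **Distribution for each participant.** "The HDI calculated as an 89% credible interval will be derived from each participant's posterior normal distribution obtained from 1000 simulations". Its centre is the participant's own change in SBP or DBP from before to after training, and its SD is half the technical error (TE/2). The change can be positive or negative.
- **ROPE.** It is set at 20% of the baseline SD of SBP and of DBP, separately by sex.

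The section closes by saying that the ROPE + HDI rule assigns the class. Neither this section nor any other requires a negative change, requires the HDI to lie below the ROPE, defines a one-sided ROPE, or provides a class for a rise.

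**The concern.** The label has a direction and the computation does not. A region centred on zero measures how far the change is from zero, not which way it went. An interval far above the ROPE and one equally far below it both have a share of zero, and a share below 1% is the only stated condition for being a responder.

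If the rule is coded as written, the count of responders adds participants whose pressure clearly rose to those whose pressure clearly fell, and presents the total as training-related hypotension. Some of those rises would be measurement noise. If an analyst instead applies the sign informally, a riser still has no class: the stated cut-off for a non-responder is more than 99% of the HDI inside the ROPE, and a clear riser has close to 0%.

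**Working it through.** The plan gives no figure for this rule, so there is nothing to reproduce. The check has two steps.

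**Inputs from the plan.** HDI level 89%; responder below 1%, likely responder below 5%, non-responder above 99%; ROPE equal to 20% of the baseline SD, read here as ± that amount.

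**Assumed inputs.** Baseline SD 8 to 12 mmHg, so a ROPE of ±1.6 to ±2.4 mmHg (0.2 × 8 = 1.6; 0.2 × 12 = 2.4); posterior SD (the plan's TE/2) 0.5 to 5.7 mmHg; SD of observed changes 4 to 7 mmHg; mean change 0 or -5 mmHg. The value 5 mmHg is the SBP difference named in the Sample size section.

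**Step 1: symmetry.** For a change d, posterior SD s and ROPE ±r, the share is the posterior probability in the overlap of the HDI, d ± 1.598s, with (-r, r), divided by 0.89. Replacing d by -d leaves it unchanged, whatever r and s are.

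The rule was also simulated as written, with 1000 draws per participant, for baseline SDs of 8, 10 and 12 mmHg and posterior SDs of 0.5, 1, 1.5, 2 and 3 mmHg. In all 15 combinations, changes of +8 and +10 mmHg had 0.0% of the HDI in the ROPE and were labelled responder, exactly as -8 and -10 mmHg were.

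The assumptions only move the change that is needed. For a rise, the share is [Φ((r - d)/s) - 0.055]/0.89. Setting it below 0.01 gives Φ((r - d)/s) < 0.0639, so the cut-off is c = r + 1.523s. With r = 2:

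- s = 1: c = 2 + 1.523 = 3.52 mmHg
- s = 2: c = 2 + 3.046 = 5.05 mmHg
- s = 5.7: c = 2 + 8.68 = 10.68 mmHg

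The same cut-offs apply to falls.

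**Step 2: how many risers.** If observed changes are Normal with mean m and SD t, the proportion of all participants who are risers labelled responder is P(Z > (c - m)/t). With r = 2:

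| Posterior SD | Cut-off c | t = 4: m = 0 | t = 4: m = -5 | t = 7: m = 0 | t = 7: m = -5 |
|---|---|---|---|---|---|
| 1 | 3.52 | 18.9% | 1.7% | 30.7% | 11.2% |
| 2 | 5.05 | 10.4% | 0.6% | 23.6% | 7.6% |
| 5.7 | 10.68 | 0.4% | <0.1% | 6.4% | 1.3% |

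Examples at the extremes: P(Z > 3.52/7) = P(Z > 0.503) = 0.307; P(Z > (3.52 + 5)/7) = P(Z > 1.217) = 0.112; P(Z > 10.68/4) = P(Z > 2.67) = 0.004.

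At m = 0 falls and rises are equally likely, so risers are exactly half of all responders in every row. The Sample size section allows for 15% drop-out, which leaves about 42 of 50 participants (50 × 0.85 = 42.5). The largest entries then correspond to about 13 people at m = 0 (0.307 × 42 = 12.9) and about 5 at m = -5 (0.112 × 42 = 4.7).

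**The case against.** The strongest reply is that the section does give a direction. It speaks of hypotensive effects when it defines the classes, and of hypotension again when it says what the percentages are for. On a natural reading the cut-offs grade evidence for a fall, and a careful analyst would not call a participant with a 10 mmHg rise a hypotensive responder. This stands in part. A reader might infer that nothing in the plan points to falls, or that the plan means to count risers as successes; the documents support neither. What they show is a label and a rule that conflict, with the sign left unwritten. The method is described briefly and rests on cited sources that are not available here, so those sources help neither side.

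Two further inferences go beyond the documents:

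- *Adverse responses would be hidden.* SBP and DBP are main outcomes, analysed as signed continuous variables in the linear mixed models, and the signed individual change is itself the input to the rule. The class label would be wrong, but the data would not be concealed.
- *A planned comparison of responder rates between men and women would be distorted.* No such comparison is specified. Sex enters this section only through the width of the ROPE.

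It is also fair to say that the size rests on assumptions and that part of it comes from elsewhere. When the posterior SD is small relative to the spread of observed changes, many participants cross the cut-off in both directions. That follows from taking TE/2 as the SD, not from the missing sign. With both SDs near 5.7 mmHg (5.66), risers labelled responders are 3.0% of participants at a mean change of zero and 0.3% at -5 mmHg.

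**Conclusion.** The point holds as a defect in the written rule. By symmetry, and whatever the variances, a rise large enough to clear the cut-off is labelled a responder just as an equal fall is. That contradicts the stated meaning of the class, and the plan offers no other class for it.

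The size cannot be fixed from the documents. With a ROPE of ±2 mmHg, a posterior SD of 1 to 5.7 mmHg and an SD of observed change of 4 to 7 mmHg, risers labelled responders are about 0.4% to 31% of participants if the mean change is zero, and from under 0.1% to about 11% if it is -5 mmHg. No single value in these ranges should be quoted as the expected error. The statement that half of all responders are risers is true only when the mean change is zero.

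The consequence is limited. The analysis is exploratory and feeds neither the mixed models nor the sample size. The correction is still worth making before data are classified, because otherwise the handling of risers is left to whoever writes the code.

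**What to change.** Add a sign condition to the rule. For responder and likely responder, require both the stated share (below 1% or below 5%) and a negative change with the HDI on the blood-pressure-lowering side of the ROPE, apart from the overlap those percentages allow. Put the mirror case in a separate class, such as BP increase, and report its count alongside the others.

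In the 15 combinations simulated, a requirement that the HDI lie below the ROPE leaves every change of -8 or -10 mmHg a responder and removes every change of +8 or +10 mmHg from that class.

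The cost is one sentence in the plan and one condition in the code, with no new data. The change does not settle two neighbouring gaps that could be closed in the same edit: participants with between 5% and 99% of the HDI inside the ROPE have no class, and the plan does not say how differing SBP and DBP classifications are combined.

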#### *Blood pressure*

Participants will be asked to wear a non-invasive inflating and deflating finger cuff during all study visits. This will allow beat-to-beat BP to be recorded using finger plethysmography (Finometer; Finapres Medical System, Amsterdam, The Netherlands) before, during, and after isometric handgrip exercise in the supine position. Beat-to-beat BP will be averaged offline over 2 to 5-min using Lab Chart 8 (ADIInstruments, BellaVista, NSW, Australia). Beat-to-beat dynamic fluctuations in BP induced by acute isometric handgrip exercise will be quantified through BP variability indices including spectral methods using the adapted HRV module of Lab Chart 8. This will give insight into sympathetic outflow to blood vessels (14,15).

**Brachial BP** of the right arm will also be measured three times at 1-minute intervals before and after isometric handgrip exercise using an automated blood pressure cuff (HEM-7311-ZSA; Omron Healthcare Co, Ltd, Kyoto, Japan) (16). Measurements will be accepted if they do not differ > 4 mmHg, and the average of the last two will be used for data analysis (16). Mean arterial pressure will be estimated as  $2/3 \text{ DBP} + 1/3 \text{ SBP}$ .

**Central BP** will be assessed via carotid artery tonometry (NIHem, Cardiovascular Engineering Inc., Norwood, MA). Brachial systolic and diastolic cuff BPs will be used to calibrate the peak and trough of the signal-averaged pressure waveforms. Carotid pressure waveforms will be calibrated with diastolic and integrated mean brachial cuff pressure. Central BP is then estimated from the calibrated carotid pressure. Central pulse pressure will be calculated as the difference between the peak and trough of the calibrated carotid pressure waveform.

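### The non-responder class cannot be reached once the posterior SD exceeds 0.128 of the baseline SD, and the plan does not show that it stays below this limit

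*Combined protocol and SAP*

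**What the plan says.** All the elements are in the Data Analysis Plan, under Individual blood pressure responsiveness to isometric handgrip training.

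- Status: "We aim to conduct an exploratory analysis of the individual BP responsiveness to isometric handgrip training".
- Interval: "The HDI calculated as an 89% credible interval", taken from 1000 normal draws centred on the participant's own pre-to-post change.
- Spread of those draws: "standard deviations calculated as TE/2, where TE is the technical error calculated as CV/2", the last expression being multiplied by 100. The section does not say whether TE is in mmHg or percent, or which repeat measurements supply the CV.
- ROPE: 20% of the baseline SD of SBP and of DBP, separately by sex. Whether this is the half-width or the full width is not written out.
- Classes: "non-responders defined as > 99 %, likely responders < 5%, and responders < 1% of HDI within the ROPE". Nothing is named for shares from 5% to 99%.

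The documents give no BP CV, TE or baseline SD. The nearest figure is the cuff rule in the Blood pressure section: "Measurements will be accepted if they do not differ > 4 mmHg, and the average of the last two will be used for data analysis".

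**The concern.** The non-responder rule asks almost the whole HDI to fit inside the ROPE. The HDI width is set by measurement error and the ROPE width by between-person spread, so whether the interval can fit at all is fixed before any training effect is seen. If it cannot fit, a participant whose BP did not move is still not a non-responder.

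The stated purpose is to separate relevant from negligible effects. If the negligible class is empty or nearly so by construction, its count says little about handgrip training. Because the ROPE uses the SD of each sex, men and women with the same true response and the same error can also show different counts.

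**Working it through.** The plan gives no expected number of responders or non-responders, so there is no figure to reproduce.

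**Inputs from the plan:** 89% HDI; cut-offs 99%, 5% and 1%; ROPE read as ±0.2 SDb, where SDb is the baseline SD; s = TE/2 with TE = CV/2 × 100.

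**Assumed:** SBP mean 115 mmHg; SDb 8, 10 or 12 mmHg; CV 2 to 6%; TE 2 to 4 mmHg. With no true change, the observed change is N(0, 2e²), where e is TE in mmHg or CV × mean.

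**Step 1: the limit.** The half-width of a normal 89% HDI is 1.598 s. The most favourable case is an observed change of exactly 0, where the share inside the ROPE is [2Φ(0.2 SDb/s) − 1]/0.89. Setting this to 0.99 gives 0.2 SDb/s = 1.559, so s ≤ 0.2/1.559 = 0.128 SDb. That is 1.03 mmHg at SDb 8 and 1.28 mmHg at SDb 10. With 1000 draws the edge is slightly soft: at a change of 0, the chance of the class is 81% at s/SDb = 0.12, 18.5% at 0.13 and about 0 from 0.14. If 20% is the full ROPE width, the limit halves to 0.064.

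**Step 2: what the limit means for each reading of s.**

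- s = CV%/4 (the formula read literally): CV ≤ 4 × 0.128 × SDb, i.e. 4.1% at SDb 8 and 5.1% at SDb 10.
- s = TE/2, TE in mmHg: TE ≤ 0.257 SDb, i.e. 2.1 and 2.6 mmHg.
- s = √2 × TE (the error of a difference between two measurements): TE ≤ 0.128/1.414 = 0.091 SDb, i.e. 0.7 and 0.9 mmHg.

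**Step 3: truly unchanged participants called non-responders.** Where only one end of the HDI is cut off, more than 99% inside means a cut-off mass below 0.0089. The tail beyond the ROPE edge is then 0.055 + 0.0089 = 0.0639 (z = 1.523), so the rule is |change| < 0.2 SDb − 1.523 s. Example at SDb 10, CV 2%: s = 0.5, the bound is 2 − 0.76 = 1.24 mmHg, the SD of the change is √2 × 2.3 = 3.25, and 2Φ(0.381) − 1 = 30%.

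| s | SDb 8 | SDb 10 | SDb 12 |
|---|---|---|---|
| CV%/4; CV 2, 3, 4, 5, 6% | 20, 8, 1, 0, 0% | 30, 14, 6, 1, 0% | 39, 20, 11, 5, 1% |
| TE/2; TE 2, 2.5, 3, 4 mmHg | 2, 0, 0, 0% | 13, 2, 0, 0% | 24, 11, 2, 0% |
| √2 × TE; TE 2 to 4 mmHg | 0% | 0% | 0% |

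In the last row the largest possible share inside the ROPE is 68% (TE 2, SDb 12: [2Φ(2.4/2.83) − 1]/0.89), against the 99% required.

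Reading across the first row shows the sex issue: with the same error and no effect, SDb 8 in one sex and 10 in the other gives 8% against 14% at CV 3%.

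**Step 4: where the other unchanged participants go.** The responder rule is met when |change| > 0.2 SDb + 1.523 s. At SDb 10, CV 4%, s = CV%/4: (2 + 1.523)/6.51 = 0.54, so about 59% are called responders. About half of these are BP rises, because the cut-offs carry no sign. About a third fall in the unnamed 5% to 99% band.

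**The case against.** A reader might infer that BP error makes the class impossible, so that the analysis returns about zero non-responders if training does nothing. The documents do not support that. They give no BP error or baseline SD, and the plan's formula halves the error twice. On the literal reading with CV 2 to 4% and SDb 10, between 30% and 6% of unchanged participants are non-responders, or about 15 to 3 of 50.

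Nor does the 4 mmHg cuff rule settle it. It is a maximum tolerance, not an error estimate, and the last two readings are averaged. If every such pair differed by the full 4 mmHg, the SD of their mean would be 4/2 = 2.0 mmHg and TE/2 would be 1.0 mmHg, just inside the limit. Between-visit error could be larger, but no figure is given.

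Three further points are fair. A strict cut-off for accepting a negligible effect is partly a design choice, and the plan cites sources for it that were not available here. The analysis is labelled exploratory. The 0% row uses an SD that the plan does not propose.

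What remains is that the class is reachable only while s is small. TE/2 is 2.8 times smaller than √2 × TE, so the class depends on understating the error of a change. Correcting s alone would empty it, so the cut-off needs its own repair. Even in the most favourable literal case at SDb 10 (CV 2%), 70% of unchanged participants are not called non-responders.

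**Conclusion.** The point holds as a conditional one. The limit s ≤ 0.128 SDb is exact for a normal posterior and a ROPE of ±0.2 SD, and it applies to SBP and DBP alike. Whether the trial crosses it depends on quantities that the plan leaves open. For SBP at SDb 10, the non-responder share under no effect runs from 30% to 0% over CV 2 to 6% on the literal formula. It is 13% at TE 2 mmHg and 0% at TE 3 mmHg or more with s = TE/2, and 0% with the actual error of a change. These shares rest on the assumed mean, SDb, CV and TE.

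A small or zero count of non-responders, or a difference between the sexes, therefore cannot be read as a training effect without knowing s relative to each sex's ROPE. The change should be made before classification is run, but its weight is limited: the analysis is exploratory, and the linear mixed models under Statistical analysis are unaffected.

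**What to change.** In the individual-responsiveness section:

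1. Define s in mmHg as √2 × TE, and name the repeat measurements from which TE is estimated. State that the ROPE is ±0.2 SD if that is meant.
2. Report for every participant the posterior probability that the fall exceeds the lower ROPE limit.
3. Replace the 99% rule with a directional one: non-responder when the HDI lies wholly above the lower ROPE limit. Use it only with the corrected s. State that only falls count as response, and label participants who meet neither rule undetermined.
4. If the 99% class is kept, state that an absence of non-responders is not interpreted when s exceeds 0.128 baseline SD.

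The first and third items belong together. For a true 5 mmHg fall (TE 2 to 4, SDb 8 to 10), the directional rule with s = TE/2 gives a false non-responder with probability 1 − Φ[(5 − 0.2 SDb + 1.598 × TE/2)/(√2 × TE)], about 4 to 14%. With s = √2 × TE it is 1 − Φ[1.598 + (5 − 0.2 SDb)/s], about 0.3 to 1.7%.

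The cost is SAP wording and a few lines of R. There are two downsides. The label changes meaning, from a negligible effect to no worthwhile fall. Many participants will also be undetermined: with the corrected s, only 1 − Φ(1.598 − 0.2 SDb/s), about 9 to 19% over the same range, of truly unchanged participants would be called non-responders.

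### The individual-response analysis labels people from an uncontrolled before-after change and never estimates whether true responses to training differ between people

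*Combined protocol and SAP*

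**What the plan says.** The section Individual blood pressure responsiveness to isometric handgrip training opens: "We aim to conduct an exploratory analysis of the individual BP responsiveness to isometric handgrip training". It sorts people by whether they show a relevant or a negligible BP-lowering effect attributed to training. The steps are:

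- **Centre:** a "posterior normal distribution obtained from 1000 simulations based on the individual pre-to-post change in SBP and DBP (delta").
- **Spread:** "respective standard deviations calculated as TE/2, where TE is the technical error calculated as CV/2", with no value given for CV or TE.
- **Draws:** "Individual normal distributions will be derived using the R's rnorm function".
- **Interval:** "The HDI calculated as an 89% credible interval".
- **Region of practical equivalence (ROPE):** "We will estimate the ROPE as 20% of the baseline SBP and DBP standard deviations in each group (sex").
- **Cut-offs:** "non-responders defined as > 99 %, likely responders < 5%, and responders < 1% of HDI within the ROPE".

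The section closes by saying that the method mitigates some pitfalls of binary response thresholds, such as not accounting for "within-participant measurement error variability associated with blood pressure or the magnitude of group differences in mean response".

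Elsewhere, the Statistical analysis section gives time, sex and training condition as fixed effects and a participant intercept as the only random effect. The Research protocol section describes a crossover with a no-exercise condition and three laboratory visits.

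**The concern.** A change from before to after training contains the common effect of training, any personal departure from it, and visit-to-visit variation. One change per person cannot separate the last two. The no-exercise change in the same people shows how much they vary without training, and the plan does not use it here. The main model does not fill the gap: with a random intercept only, it estimates no between-person variance in the training effect.

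At stake is the interpretation. A table of responders and others invites the conclusion that people differ in how they respond. In a study of sex effects, with a ROPE set separately by sex, it also invites a comparison of responder counts between men and women. Neither conclusion follows from the labels alone.

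**Working it through.** **1. What enters the calculation.** Three quantities enter: the person's own delta, a technical-error SD, and the sex-specific baseline SD (through the ROPE). The last is a group quantity, but it describes baseline spread, not mean response. No mean-response term appears, so the second half of the closing claim has no counterpart in the method. The first half, measurement error, does enter through TE.

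**2. Inputs for a numerical check.** The plan gives no numerical result for this analysis to reproduce. From the documents: 89% HDI, cut-offs of 1%, 5% and 99%, ROPE of 0.2 baseline SD, and 5 mmHg (the SBP difference in the Sample size section). Assumed, because the documents give no figures: baseline SBP SD 9 mmHg, so ROPE = ±0.2 × 9 = ±1.8 mmHg, read as centred on zero; and an error SD of a change, s, of 4 to 7 mmHg, used both to generate the data and in the rule. The written cut-offs carry no sign; a fall in BP is required here because the section concerns hypotensive effects.

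**3. Thresholds.** The 89% HDI is delta ± 1.598s. Less than 1% of it inside the ROPE means less than 0.01 × 0.89 = 0.0089 of probability between -1.8 and the upper end. Since 0.945 - 0.0089 = 0.9361 and z(0.9361) = 1.523, a responder has delta < -1.8 - 1.523s. For 5%: 0.945 - 0.0445 = 0.9005 and z = 1.284, so responder or likely responder needs delta < -1.8 - 1.284s.

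**4. Everyone has the same true change.** With delta ~ N(-5, s²), the responder share is Φ((3.2 - 1.523s)/s). For s = 5: Φ(-0.883) = 18.9%. Undecided means 5% or more of the HDI lies in the ROPE.

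| s (mmHg) | Responder | Likely responder | Rise, under 5% in ROPE | Undecided | Responder if true change is 0 |
|---|---|---|---|---|---|
| 4 | 23.5% | 7.9% | 0.1% | 68.5% | 2.4% |
| 5 | 18.9% | 7.1% | 0.4% | 73.6% | 3.0% |
| 6 | 16.1% | 6.5% | 0.8% | 76.6% | 3.4% |
| 7 | 14.3% | 6.1% | 1.2% | 78.4% | 3.8% |

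Nobody reaches the non-responder cut-off. The largest possible share inside the ROPE, at delta = 0, is (2Φ(1.8/s) - 1)/0.89, which is 39% at s = 4 and 23% at s = 7, far below 99%.

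**5. How much of a personal deviation is real.** The weight is SD_IR²/(SD_IR² + s²), where SD_IR is the true SD of individual response. If SD_IR is 3 mmHg, it is 9/(9 + 25) = 0.26 at s = 5 and 9/(9 + 49) = 0.16 at s = 7. The plan's distribution gives a weight of 1.

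**6. What the trial could estimate.** Completers: 50 × 0.85 = 42.5, taken as 42. Assume a single-visit error SD of 4.2 mmHg, so a change has SD √2 × 4.2 = 5.94 and variance 35.28. Training and control changes that share visit 1 correlate at 0.5. With no true heterogeneity, the standard error of the variance difference is 35.28 × √(4 × 0.75/41) = 9.54. Then 1.96 × 9.54 = 18.7, and √18.7 = 4.3, so the estimated SD_IR ranges over about ±4.3 mmHg; simulation gives -4.3 to about +4.4. Simulated detection at two-sided 5% is about 44% at a true SD_IR of 5 mmHg, about 12% at 3 mmHg, and about 24% at 5 mmHg within one sex (21 people). With a single-visit SD of 5 mmHg, detection falls to about 29% at 5 mmHg and 9% at 3 mmHg.

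**The case against.** The strongest defence is that the plan asks a different question: whether each person's change is relevant or negligible against a ROPE, not whether people differ from each other. This largely stands, and it rules out several stronger readings.

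- A reader might infer that the rule creates false responders. Under a common change of -5 mmHg and a ROPE of ±1.8, every responder label is correct and the others are undecided, not wrongly called non-responders. With no true effect and a correctly sized error SD, only about 2% to 4% are labelled responders.
- Larger responder shares, such as 44% to 63% under the same -5 mmHg, arise when the rule uses an error SD of 1.25 to 2.5 mmHg. That is a question about the size of TE/2 and is separate from this point.
- A reader might say the distribution is no posterior, or that noise is ignored. With a flat prior and a known error SD it is a valid posterior for one person, and TE and the ROPE do allow for noise.
- The section announces no male-female comparison of responder counts; that is a foreseeable use, not a stated one. The wording on group differences is ambiguous, and the text claims only to mitigate some pitfalls.

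The analysis is also exploratory, and neither the sample size nor the main mixed-model results depend on it. What survives is the attribution: calling an individual's effect training-related needs the no-training change, and reading different labels as different responses needs a between-person variance that nothing in the plan estimates.

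**Conclusion.** The point holds in a limited form. The labels rest on an uncontrolled individual change, and the plan nowhere estimates whether training changes vary more between people than no-training changes. With identical true responses of -5 mmHg, about 14% to 24% would be responders and about 68% to 78% undecided, so variation in labels is not evidence of variation in response. These percentages depend on the assumed baseline SD of 9 mmHg and error SD of 4 to 7 mmHg; the documents supply neither. The statement about group differences in mean response is not supported by the method described. Because the analysis is exploratory, the priority is low.

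**What to change.** In the section on individual responsiveness:

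1. For SBP and DBP, report the SD of individual response, the signed square root of SD_training² - SD_control², with a 95% CI, overall and by sex.
2. Compute it with allowance for sequence and period. With three visits, training-first participants reach the control visit only after training and a 4-week washout, so their change from visit 1 to control is not clearly a no-training change. For control-first participants, visit 1 to the training visit spans both periods. Add a sensitivity analysis for carry-over, for example taking the no-training change from control-first participants only.
3. Present the result beside the responder counts. If the CI includes 0, state that individual differences in response were not shown, not that they are absent. Do not make publication of the counts conditional on the CI: detection is low enough that such a rule would often suppress them when moderate heterogeneity is real.
4. Give individual estimates shrunk toward the group training effect as a sensitivity analysis.
5. Correct or delete the claim about group differences in mean response.

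The cost is SAP wording and a few lines of R on data already collected. The drawback is imprecision: a 95% range of about -4.3 to +4.4 mmHg when the truth is 0, worse within one sex and in the control-first subset. The likely conclusion is therefore a cautious one.
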